13.1.9. Handling of Dropouts or Missing Data

Subjects who discontinue investigational product are expected to continue in the study until study termination.

Missing data will be assumed to be missing at random. In order to determine the effect of missing data on the analysis, efficacy endpoints will be analyzed using different methods of imputation as described below. In addition, the same analyses for primary and key secondary endpoints based on ITT and PP populations will be performed to assess robustness of analysis results. During the conduct of the study, the DMC may recommend refining the missing data strategy to better address the observed pattern of missing data, based on blinded monitoring of the data.

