5.7. Summary of Known Potential Risks with OCA

The rate of progression and risk of decompensation is variable and may be rapid in certain patients, necessitating closer surveillance of patients at risk.

Clinical Data

In two Phase 2 studies and a Phase 3 study evaluating OCA in the treatment of subjects with PBC, hepatic adverse events, including jaundice, worsening ascites and primary biliary cholangitis flare, were observed in subjects receiving doses of OCA ranging from the maximum approved dose of 10 mg once daily to 50 mg (5 times the highest recommended dose), as early as one month after starting treatment with OCA.

In addition, safety findings in NASH clinical trials include 2 cases of hepatic decompensation reported as SUSARs, 1 of which resulted in death. Both cases involved numerous confounding factors that make evaluation of association with treatment difficult. Details for both events are provided in the current version of the OCA Investigator's Brochure.

The primary AE shown to be related to OCA is pruritus. Pruritus has also been observed in clinical studies with OCA in other indications, as well as in healthy subjects, with the highest frequency observed in subjects with PBC. The incidence and severity of pruritus have been shown to be dose dependent, but there is no evidence of association with stage or progression of underlying disease.

Changes in lipid profiles have also been observed with OCA dosing, including an increase in low density lipoprotein (LDL) cholesterol and a decrease in high-density lipoprotein (HDL) cholesterol. The clinical significance of these lipid findings remains unclear and is being studied further.

An independent data monitoring committee (DMC) has performed detailed reviews of individual subject and aggregate data from both the Phase 3 clinical outcomes study in subjects with PBC (Study 747-302) and the Phase 3 pivotal studies in subjects with NASH fibrosis (Study 747-303) and NASH cirrhosis (Study 747-304) on a quarterly basis, in an unblinded fashion, and in closed sessions (without the Sponsor's participation). In the quarterly DMC meetings to date, the DMC has recommended the studies continue without modification.

Following a request from the FDA to provide an up-to-date DMC report analyzing unblinded data on respective incidence of cholecystitis, cholelithiasis, and pancreatitis by treatment group across all ongoing clinical studies, an ad hoc DMC review was held and the DMC recommended that:

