9.4.1. Unblinding Procedures – Emergency Unblinding Procedures

Treatment assignment for individual subjects will be made available to the Investigator for medical emergency use only (such as unblinding which is necessary in order to treat an SAE) through the IWRS system. When possible, the Medical Monitor should be consulted in the event that a medical emergency necessitates unblinding (ie, in situations where knowledge of the blinded treatment assignment is necessary for further medical management of the subject). If it is not reasonable to inform the Medical Monitor in advance of the unblinding, the Investigator must promptly document in the subject's record the rationale for unblinding and should subsequently contact the Medical Monitor to explain any premature unblinding of treatment assignment. Procedures for unblinding a subject's treatment will be provided separately to the Investigator. Similarly, if the Medical Monitor breaks the blind for an individual subject for the purpose of evaluating an emergent safety issue, the Medical Monitor will document within trial documentation the rationale, circumstances, and the person or persons being informed about the unblinding.

The DMC will have access to the IWRS and will be able to unblind individual subjects. Refer to [Section 13.3](#) for further details regarding DMC access to blinded and unblinded data. The DMC will document details about any unblinded subject data reviews in the closed session DMC minutes, which will be made available to the Sponsor only after the database is locked and the trial is unblinded. Cases of premature unblinding, as noted above, will also be reviewed by the DMC.

Access to treatment assignments will also be made available to the designated Intercept staff responsible for expedited safety reporting of suspected unexpected serious adverse reactions (SUSARs) to the Regulatory Authorities.

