12.1.6. Suspected Liver-Related Clinical Outcome Events

Specified liver-related clinical outcome events may, by definition qualify as SAEs (see [Section 12.1.1.2](#)). The Sponsor must be notified of any SAEs within 24 hours of the site becoming aware of the event (see [Section 12.1.5.2](#)). The Sponsor is responsible for regulatory reporting of SAEs, including expeditious reporting of SUSARs, which are defined as SAEs that are considered related (definitely, probably, or possibly related) to the investigational product and considered unexpected as defined in the IB.

Given that the liver-related clinical outcome events may also meet the criteria of a SUSAR, but are considered in aggregate as part of the primary endpoint and the DMC reviews of all safety and efficacy data approximately quarterly, the Sponsor will not expeditiously report suspected liver-related clinical outcome events in order to retain the study blind and preserve the integrity of the clinical outcomes endpoint. These events will be selected as a “study event” on the AE CRF and will be submitted for adjudication to the Hepatic Outcomes Committee as described in [Section 13.4](#).

The Sponsor will consider the following list of clinical outcome events (MedDRA preferred terms) to be disease related and exempt from expeditious regulatory reporting, but will continue to report them in a nonexpeditious manner: death, end-stage liver disease (preferred term: chronic hepatic failure), liver transplant (preferred term: liver transplant), HCC (preferred term: hepatocellular carcinoma), variceal bleeding (preferred term: gastroesophageal variceal haemorrhage or oesophageal varices haemorrhage), hepatic encephalopathy (preferred term: hepatic encephalopathy), spontaneous bacterial peritonitis (preferred term: peritonitis bacterial), ascites (preferred term: ascites), and histological or clinical progression to cirrhosis (preferred term: hepatic cirrhosis).

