13.1.12. Continuous Monitoring and Interim Analyses

Blinded safety reports including the accrual of events, drop outs, and/or loss of subjects to commercially available OCA will be reviewed by the DMC on a regular basis.

Two planned interim analyses of the liver-related outcomes will be conducted using the Lan-DeMets O'Brien-Fleming boundaries ([Reboussin 2000](#)). Both interim analyses will be pre-specified and will occur after accrual of 50% (64 events) and 75% (96 events) of clinical outcome events, respectively.

The DMC will review the available efficacy data in conjunction with detailed safety data and other relevant information to recommend continuation, modification, or cessation (for efficacy)

of the study beyond each interim analysis. Modification of the study would not take place without prior agreement with regulatory authorities.

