13.3. Data Monitoring Committee

An independent DMC that includes hepatologists, pharmaceutical physicians, epidemiology/cardiology expert(s), and statistician(s) not involved in the study as Investigators, adjudication committee members, or consultants. The DMC will have oversight over the study

conduct as defined by the DMC charter. All members will have considerable experience with clinical study conduct and DMCs. Any candidate found to have a conflict of interest or whose name is listed on the FDA debarment list will not be offered membership. Conflicts of interest will be assessed regularly, and if members are found to have a new conflict of interest they will be replaced.

The DMC will meet approximately quarterly at scheduled meetings and ad hoc meetings will be convened, as appropriate, to review safety and efficacy data in order to ensure the safe and proper treatment of subjects. Based on review of these data, the DMC will advise the Sponsor on the validity and scientific merit of continuing the study.

Written minutes of both the open and closed DMC sessions will be prepared. The closed minutes will be made available to the appointed Sponsor representatives only after the database is locked.

Data listings provided to the DMC do not contain individual subject treatment information; however, the DMC will have access to the database and may unblind individual subject data as appropriate. Summary tables reviewed by the DMC during closed sessions will include an overall column containing information regarding all subjects and separate treatment columns with 'dummy' labels, ie, the actual treatment groups are used, but are not identified. Data reviewed during the meetings will include, at a minimum, disposition, demographics, exposure, clinical laboratory results, Medical Dictionary for Regulatory Activities (MedDRA) coded AEs, and AEs leading to early withdrawal of investigational product. At each meeting, detailed narratives of interval SAEs (including events resulting in death) are reviewed by the DMC in addition to a cumulative list of all SAEs.

The DMC may agree to adjust meeting frequency based upon actual and projected safety and efficacy data availability. Adjustments to or stopping of the protocol defined doses may be considered based on DMC evaluation of OCA safety and tolerability.

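### Section 13.1.9 calls a DMC recommendation on the missing-data strategy blinded, but the protocol gives the DMC by-arm data and nothing separates the two

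*Protocol*

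**What the plan says.** Section 13.1.9 (Handling of Dropouts or Missing Data) provides that, while the study is running, the "DMC may recommend refining the missing data strategy to better address the observed pattern of missing data, based on blinded monitoring of the data". It names no other body to make the proposal and sets no date after which the strategy is closed.

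The protocol describes the DMC's access to data in these places:

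- Section 5.7 reports that the DMC has reviewed individual and aggregate data from this study and two NASH studies "on a quarterly basis, in an unblinded fashion, and in closed sessions".
- Section 9.4.1: "The DMC will have access to the IWRS and will be able to unblind individual subjects".
- Section 13.3: "the DMC will have access to the database and may unblind individual subject data as appropriate". Its closed-session summary tables carry "separate treatment columns with 'dummy' labels, ie, the actual treatment groups are used, but are not identified".
- Section 12.1.6 relies on the fact that "the DMC reviews of all safety and efficacy data approximately quarterly".
- Section 13.1.12, on the interims at 64 and 96 events: "The DMC will review the available efficacy data in conjunction with detailed safety data".

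Section 13.1.12 also opens with a blinded stream, which is to recur throughout the trial: "Blinded safety reports including the accrual of events, drop outs, and/or loss of subjects to commercially available OCA will be reviewed by the DMC".

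Two safeguards are stated. Under Section 13.1.8 the planned primary analysis is not revised without prior agreement of the regulators. Under Section 13.1.12 the same holds for modification of the study.

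**The concern.** The rules in Section 13.1.9 and its subsections decide how subjects with incomplete follow-up enter the efficacy analyses. Section 13.1.9.1 covers the primary time-to-event analysis: censoring at last contact, and an event on Day 1 for subjects with no data after randomization. Section 13.1.9.2 covers the ANCOVA endpoints, which include two of the key secondary endpoints.

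A change to such rules during a trial is harmless when those proposing it have seen only pooled data. It is not harmless when they have seen results by arm. Dropout here may well differ by arm: subjects may leave investigational product for commercial OCA (Sections 8.4.1 and 9.2.1), and Section 5.5.2.3 acknowledges possible bias from that source. A committee with by-arm tables would see exactly that pattern. At stake is whether the Sponsor could later demonstrate that a changed rule was chosen independently of the results, even if the committee acted impeccably.

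**Working it through.** **Design figures.** The point rests on no figure in the protocol, but the design figures do reproduce. Inputs from Section 13.1.2: hazard ratio 0.60, two-sided 5%, 80% power, 1:1 allocation, placebo survival 0.6 at 8 years, 4 years of accrual plus 6 of follow-up, 10% dropout.

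- Freedman: (1.960 + 0.842)² × [(1 + 0.6)/(1 − 0.6)]² = 7.849 × 16 = 125.6, so 126 events. Schoenfeld: 4 × 7.849/(ln 0.6)² = 120.3, so 121.
- Power at 127 events with Lan-DeMets O'Brien-Fleming looks at 64, 96 and 127 is 79.7% (Freedman drift) or 81.3% (Schoenfeld drift), against the stated 80%.
- The mean event probability over the two arms is 0.331, so 127/0.331 = 384 subjects, and 384/0.9 = 427 against the stated 428.
- 10% dropout is 0.10 × 428 ≈ 43 subjects.

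**The passages side by side.**

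1. Section 13.1.9 needs a proposer who is blind to arm-level results.
2. Section 5.7 says the DMC's quarterly reviews were unblinded. Section 13.3 says arms are shown separately but not named. The two differ on masking and need reconciling. On either account the DMC sees data by arm, and it can break the code.
3. Sections 12.1.6 and 13.1.12 give it efficacy data, routinely and at the interims.
4. The blinded reports in Section 13.1.12 cover dropouts and loss to commercial OCA, and are probably what Section 13.1.9 has in mind. They go to the same members. No sentence assigns the two streams to different people or requires the proposal to come before the by-arm review.
5. The protocol does separate roles elsewhere. Section 13.1.2.1 bases event monitoring on pooled counts with no knowledge of comparative efficacy. Section 13.1.8 gives propensity modelling to a third-party statistician separate from those doing the efficacy analyses. Section 13.1.9 has no such separation.

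**Illustration of size.** Assumptions, none of them in the protocol: two candidate rules give null test statistics Z₁ and Z₂ with correlation ρ, the more favourable rule is always adopted, and other interim effects are ignored. If the choice is made knowing the final statistics, the one-sided error is P(max(Z₁, Z₂) > 1.96) = 1 − Φ₂(1.96, 1.96; ρ). If it is made on the 64-event interim, each final statistic is √(64/127) × interim part + √(63/127) × later part, and the rule that leads at the interim is kept (simulation, 8 million replicates).

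| ρ | Final results known | Chosen at 64 events |
|---|---|---|
| 0.90 | 3.5% | 3.2% |
| 0.95 | 3.2% | 3.0% |
| 0.98 | 3.0% | 2.8% |
| 0.99 | 2.8% | 2.7% |

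The nominal value is 2.5%. A choice made on pooled, blinded data would not produce this inflation.

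**The case against.** The best defence is that Section 13.1.12 supplies the blinded dropout reports, so the phrase in Section 13.1.9 has a coherent meaning, and that the DMC charter, which is not shown, may keep the roles apart. Section 13.3 also masks the arm labels and provides for unblinding only as appropriate, and the unblinded wording of Section 5.7 comes from a background summary covering three studies. This stands in part: the intended source is identifiable. But a blinded report does not blind a reader who also holds results by arm, and the protocol itself asserts that the recommendation is blinded.

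The second defence is that pre-specification is already strong. Section 13 requires the SAP to be approved before the first interim, Section 13.1.9.1 states the primary rule, Section 13.1.9.2 makes observed cases primary for the ANCOVAs, and subjects who stop product are to stay in follow-up. This is correct, and it means the choice of missing-data rule cannot be called the most influential one left open; nothing in the document shows that. Section 13.1.9 nonetheless allows the strategy to be revisited after that approval, with no cut-off.

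A reader might also infer that people who know the results can themselves change the primary analysis, or that the DMC conducts the interims. The text does not support either: the DMC recommends, it reviews the interim data, and Sections 13.1.8 and 13.1.12 require regulatory agreement first.

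**Conclusion.** The point holds as an internal contradiction with a limited consequence. Section 13.1.9 describes as blinded a recommendation from a body to which the protocol gives by-arm data, unblinding rights and efficacy results. Such a recommendation cannot be shown to be independent of the results.

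Regulatory agreement limits what can follow but does not make the recommendation blind. Section 13.1.8 names only the primary analysis in its safeguard, so the key secondary analyses are not expressly covered by it.

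The 2.8–3.5% range is illustrative and assumes deliberate choice of the favourable rule. A lower assumed correlation gives more (0.7 gives about 4.2%), but that value is implausible: with about 10% dropout, two rules would share some 90% of subjects. The conclusion does not depend on any of these figures. The change should be made. It also does not depend on the SAP, because the statement is in the protocol.

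**What to change.** Replace the sentence in Section 13.1.9 with:

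> Any refinement of the missing-data strategy will be proposed by blinded Sponsor statisticians from pooled data without treatment codes and documented in a dated SAP version or amendment before the first interim analysis; the DMC will not propose changes to the missing-data strategy.

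If the first interim has already taken place, remove the DMC's role and justify any later change from pooled blinded data only. Align the DMC charter, and reconcile Sections 5.7 and 13.3 on how masked the routine closed tables are.

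Keep the restriction to the missing-data strategy. Section 13.1.8 separately lets the DMC recommend a revised primary efficacy analysis after an interim. A ban on any DMC comment on the efficacy analysis would contradict that provision, so cross-refer to it and leave it unchanged.

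The cost is one protocol sentence and one charter line; the blinded pooled review of Section 13.1.2.1 already exists and can carry the work. The downside is that the DMC can no longer steer this choice after the interims.

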13.1.9.1. Time to Event Endpoints

For the time to event analyses, subjects who do not experience an event will be censored at the time of their last contact. Subjects with no data after randomization will be considered to have an event on Day 1 (first day of investigational product dosing).

For analyses of the percentage of subjects with an event, subjects with no data after randomization will be considered to have an event.

All time to event endpoints include only adjudicated events. Sensitivity analyses may consider all events regardless of adjudication. Events with discrepant adjudication will be analyzed using both results.

13.1.9.2. Quantitative Endpoints

For efficacy endpoints that utilize an ANCOVA model, observed cases will serve as the primary analysis. Sensitivity analyses to assess the effect of missing data may be conducted where missing data is imputed using last observation carried forward.

Sensitivity analyses of ANCOVA models will also be evaluated using a restricted maximum likelihood based mixed-effect repeated measures model where no imputations will be made for missing values.

13.1.9.3. Responder Endpoints

In an efficacy analysis in which subjects are classified as either a responder or a non-responder (binary outcome) based on dichotomizing a continuous variable, any subject who does not provide an assessment at the specified timepoint for the defining of response will be considered to be a non-responder. That is, for the percentage of responders, the subject will be included in the denominator and will not contribute to the numerator.

For sensitivity analyses using only “observed cases,” subjects who do not provide an assessment at the specified timepoint for the defining of response will not be included. That is, for the percentage of responders, the subject will not be included in the numerator or the denominator.

13.1.10. Multiple Comparisons/Multiplicity

The key secondary efficacy endpoints are as follows:

- Time to MELD score ≥ 15
- Time to first occurrence of liver transplant or death (all-cause)
- Change from Baseline in total bilirubin at end of study
- Change from Baseline in ALP at end of study

The hypothesis testing of key secondary analyses will compare placebo and OCA and will be conducted in a sequential closed testing gate-keeping procedure (in the order in which the key secondary endpoints are stated above), provided that the primary efficacy endpoint comparison is statistically significant in favor of OCA. If the primary comparison is not statistically significant then comparison of the secondary endpoints will be considered as descriptive and exploratory.

This procedure controls the study-wise type I error.

- First (step 1) placebo and OCA will be compared with respect to the primary efficacy endpoint. If the comparison achieves statistical significance at 2-sided 0.05 level in favor of OCA group, then
- The time to MELD score ≥ 15 will be compared between placebo and OCA (step 2). If the comparison achieves statistical significance at 2-sided 0.05 level in favor of OCA group, then
- The time to liver transplant or death (all-cause) will be compared between placebo and OCA (step 3). If the comparison achieves statistical significance at 2-sided 0.05 level in favor of OCA group, then
- Change from Baseline in total bilirubin will be compared between placebo and OCA (step 4). If the comparison achieves statistical significance at 2-sided 0.05 level in favor of OCA group, then
- Change from Baseline in ALP at the end of study will be compared between placebo and OCA (step 5).

If at any step defined above the comparison is not statistically significant at the 2-sided 0.05 level then the remaining comparisons in the stated hierarchy will be considered descriptive and exploratory. The study-wise type I error will be maintained with the above closed procedure.

Additional efficacy endpoints will be analyzed; however, hypothesis tests will be applied for descriptive and exploratory purposes only.

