13.1.2. Determination of Sample Size

The target population is subjects who are at higher risk of liver-related clinical complications. Eligible subjects will have a diagnosis of PBC with bilirubin levels $>ULN$ and $\leq 5x ULN$ and/or $ALP > 3 \times ULN$. The following assumptions were used in sample size calculations:

- Exponential survival curves, placebo survival estimate of 0.6 at 8 years with a hazard ratio of 0.60, and total study duration of 10 years (from first subject enrolled), allowing for 4 years of subject accrual and 6 years of follow up.
- Subjects will be randomized in a 1:1 ratio to placebo or OCA.
- The 2 groups will be compared using a 2-sided log rank test at the 5% level of significance.
- Two interim analyses and one final analysis are planned. The first interim analysis will be performed when 50% of the target events are accrued and the second interim will be performed when 75% of the target events are accrued.
- A dropout rate of 10% is assumed

Based on the randomization ratio, significance level, and assumed hazard ratio, a total of 127 events (both groups combined) will provide 80% power to demonstrate a statistically significant difference between OCA and placebo on time to liver-related outcomes, including all-cause mortality.

In addition, based on the remaining assumptions stated above, it is estimated that approximately 428 subjects will be enrolled to attain 127 events.

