13.1.4. Key Secondary Efficacy Analyses

The key secondary efficacy endpoints will compare OCA to placebo on the following:

- Time to first occurrence of MELD score ≥ 15

- Time to liver transplant or death (all-cause)
- Change from Baseline in total bilirubin at end of study
- Change from Baseline in ALP at end of study

The key secondary efficacy analyses will compare OCA to placebo in the ITT population with respect to the key secondary efficacy endpoints. Only adjudicated events will be included in time-to-event analyses. The comparison (hypothesis testing) will be conducted as specified in [Section 13.1.10](#) in a sequential closed testing gate-keeping procedure, provided that the primary efficacy endpoint comparison is statistically significant in favor of the OCA treatment group. If the primary comparison is not statistically significant then comparison of the secondary endpoints will be considered as descriptive and exploratory. This procedure controls the study-wise type I error.

The 2 treatment groups will be compared using the same methodology as specified for the primary efficacy analysis ([Section 13.1.3](#)). The same analyses for key secondary efficacy endpoints will be performed for PP population as a sensitivity analysis.

Analyses of change from Baseline to end of study in ALP and total bilirubin will be compared between treatment groups using analysis of covariance (ANCOVA) with change from Baseline as the dependent variable including treatment group and randomization stratification factor as fixed effects and the Baseline values as a covariate. The same analysis will be carried out using percentage change from Baseline as the dependent variable.

Descriptive statistics of the laboratory values will be summarized by treatment group. The results, change from Baseline, and percentage change from Baseline values, as well as estimates of least-square means, standard errors, and 95% CIs, will be presented by treatment group. Estimates of the mean difference between treatment groups, the standard error of the difference, and 95% CI of the difference will be presented.

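### Section 13.1.10 tests each gatekeeping step at a flat 2-sided 0.05 and claims study-wise error control, without reference to the two alpha-spending efficacy interims in 13.1.12

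*Protocol*

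**What the plan says.** **Section 13.1.10 (multiplicity).** Step 1 compares the arms "with respect to the primary efficacy endpoint. If the comparison achieves statistical significance at 2-sided 0.05 level" in favour of OCA, and the procedure then moves to time to MELD score of 15 or more. Time to transplant or death, change in bilirubin and change in ALP follow in order. If any comparison is "not statistically significant at the 2-sided 0.05 level then the remaining comparisons in the stated hierarchy" become descriptive. The section concludes: "The study-wise type I error will be maintained with the above closed procedure". Section 13.1.4 makes the same claim ("This procedure controls the study-wise type I error") and refers to 13.1.10 for the testing rule.

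**Section 13.1.12 (interims).** "Two planned interim analyses of the liver-related outcomes will be conducted using the Lan-DeMets O'Brien-Fleming boundaries". They "will occur after accrual of 50% (64 events) and 75% (96 events) of clinical outcome events". The DMC may "recommend continuation, modification, or cessation (for efficacy").

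**Section 13.1.2 (sample size).** The groups are "compared using a 2-sided log rank test at the 5% level of" significance, listed beside the two interims and one final analysis, with 127 events for 80% power at a hazard ratio of 0.60.

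Section 13.1.10 mentions neither the interims nor the boundaries. Section 13.1.12 mentions neither the hierarchy nor a final critical level.

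**The concern.** A fixed-sequence test at 0.05 per step controls the familywise error when everything is tested once. This trial can be analysed for efficacy at three times, so two things can go wrong.

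1. **Primary.** Part of the 0.05 is spent at the interims. A further 0.05 at the final look exceeds the total, and 13.1.10 and 13.1.12 then give opposite answers for some p-values.
2. **Key secondaries.** The gate protects a null secondary only while the primary is also null. When OCA works on the primary, the gate opens at a look chosen by the data. A secondary correlated with the primary is then tested at full level at a time when the primary has run favourably.

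At stake are the declaration of success in a confirmatory outcomes trial and the status of the key secondary claims.

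**Working it through.** **Inputs.** Overall 2-sided alpha 0.05, hazard ratio 0.60, 1:1 allocation, 127 events, 80% power (Section 13.1.2); looks at 64, 96 and 127 events with Lan-DeMets O'Brien-Fleming boundaries (13.1.12); 2-sided 0.05 at each step (13.1.10). The correlations between the primary and a key secondary are assumptions, because the Protocol gives none.

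**1. The plan's own figure.**
- Schoenfeld, fixed design: 4 × (1.960 + 0.842)² / (ln 0.60)² = 120.3, so 121 events.
- Freedman, fixed design: (1.960 + 0.842)² × (1.60/0.40)² = 125.6, so 126 events.
- The two interims inflate these by 1.020, to 123 and 129.
- With the spending boundaries in force, 127 events give 81.3% power (Schoenfeld) or 79.7% (Freedman).

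The stated 127 events for 80% therefore reproduces with alpha spending applied.

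**2. Boundaries.** Spending function with 0.025 per tail: α(t) = 4 × [1 − Φ(2.241/√t)]. Critical values come from numerical integration of the joint distribution of the three statistics.

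| Look | t | Cumulative alpha | Critical Z | Nominal 2-sided p |
|---|---|---|---|---|
| 64 | 0.504 | 0.0032 | 2.949 | 0.0032 |
| 96 | 0.756 | 0.0199 | 2.348 | 0.0189 |
| 127 | 1 | 0.0500 | 2.016 | 0.0438 |

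**3. Primary, read literally.** Keep the two interim boundaries and use 1.960 at the final look. The interims spend 0.0199. The chance of first crossing 1.960 at the final look is 0.0356. Total: 0.0199 + 0.0356 = 0.0555. The alternative 2-sided form of the spending function gives 0.0578.

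**4. Key secondaries, primary boundaries correct.** Paths of the primary and of a null secondary were simulated. The secondary was tested once at 2-sided 0.05 at the look where the primary crossed. The figure shown is the largest one-sided error over the size of the primary effect.

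| Assumed correlation | Worst-case one-sided error (target 0.025) |
|---|---|
| 0 | 0.025 |
| 0.5 | 0.028 |
| 0.7 | 0.030 |
| 0.8 | 0.032 |
| 0.9 | 0.034 |

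Steps 2 and 3 must be positively correlated with the primary, because MELD score of 15 or more, transplant and death are among its components.

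**5. Is early stopping remote?** No. At a hazard ratio of 0.60 the chance of crossing at one of the two interims is about 57%.

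**The case against.** **The 0.05 may be the overall level.** A Lan-DeMets boundary fixes the final critical value once the overall alpha is set. Section 13.1.2 lists the 5% level beside the interims, and the event count reproduces with spending applied. This is a fair reading. It removes the excess error for the primary and leaves a missing cross-reference there. It does not help steps 2 to 5, where no boundary is stated at all.

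**The detail may sit in the SAP.** A boundary table can. But the Protocol states a level for each step and asserts a property of that procedure. A SAP that used about 0.044 for the primary would depart from the wording of 13.1.10.

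**The secondary inflation is conditional.** This stands. Section 13.1.10 gives no testing time for steps 2 and 3, steps 4 and 5 are end-of-study changes, and the DMC only recommends. If the trial runs to 127 events and the hierarchy is tested once there, a flat 0.05 adds no error to the secondaries. The range of correlations is assumed, and nothing in the Protocol supports high values for bilirubin or ALP.

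**Stronger readings that do not hold.**
- A reader might infer 0.05 at all three looks, which would give 0.097. Section 13.1.12 rules that out.
- A reader might infer that the interims came in with Version 4 and the gate was overlooked. Appendix H shows both interims already in the Version 3.1 text, and Appendix I, which logs them as new against Version 3, omits minor edits, so the history cannot be settled.

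**Conclusion.** The rule and the claim in 13.1.10 do not fit together once 13.1.12 is in force; the section is wrong as written.

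- **Literal reading:** the primary's overall 2-sided error is about 0.0555, an excess of about half a percentage point. The two sections disagree for a final p between about 0.0438 and 0.05.
- **0.05 as the overall level:** the primary is controlled, but the study-wise claim still fails for key secondaries tested at a flat 0.05 after an early efficacy stop. The worst-case one-sided error is about 0.028 to 0.034 at correlations of 0.5 to 0.9, and there is no excess at correlation 0.

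The boundary figures assume looks at exactly 64, 96 and 127 events and 0.025 spent per tail. The documents do not support calling this unadjusted testing at every look, or saying that the secondaries are inflated whatever happens.

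**What to change.** In Section 13.1.10:

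1. State that 0.05 is the overall 2-sided level.
2. Replace the step 1 criterion with crossing the Lan-DeMets O'Brien-Fleming boundary at that analysis (final nominal p about 0.044, recomputed from the actual event counts).
3. Test each key secondary against its own alpha-spending boundary at the look where the primary crosses, instead of a flat 0.05. Each needs its own information fraction: events for the two time-to-event endpoints, subjects with data for bilirubin and ALP. Primary event counts do not measure information for the two ANCOVA endpoints.

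Section 13.1.4 needs no change of level; it states none and refers to 13.1.10.

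**Cost.** Wording only, to be settled before the first interim. Thresholds become slightly stricter: the final critical hazard ratio moves from exp(−2 × 1.960/√127) = 0.706 to exp(−2 × 2.016/√127) = 0.699. Planned power at 127 events is about 81% (Schoenfeld) or about 80% (Freedman), so no events need to be added.
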